- CC first, OC at 3 years for those patients with negative initial CC
- Annual FIT for 2 years, colonoscopy at 3 years for those patients with negative FIT during the study

To do this, we will adapt the model according to these three strategies and update parameters using:

- Data from FAMCAP study, especially patient compliance to tests,
- Data from literature,
- And if necessary, expert opinions.

Economic evaluation design

The design retained for the economic study is a cost-effectiveness analysis, which provides information on the additional cost per additional effectiveness. Incremental cost-effectiveness ratio will be calculated based on the incremental cost and the incremental effectiveness of each compared couple of strategies.

Viewpoint for analysis and time horizon

The analysis will be conducted from the viewpoint of the French Public Health Insurance on a lifetime horizon.

Cost

We will take into account only hospital costs because CRC patient are essentially cared at a hospital.

Hospital costs include mainly screening, surveillance procedures and CRC treatment costs.

Consumed resources will be identified according to Hassan et al. study (2011), French guidelines and colorectal cancer experts.

Hospital stays will be valued by the current tariff of the corresponding hospital stay related group (GHS).

For external acts, we will use the current tariffs of the Common Classification of Medical Acts (CCAM) and those of the general classification system for the professional activities (NGAP) for consultations.

Measure of effectiveness and ICER

The clinical effectiveness will be measured in terms of life-years gained so that the incremental cost-effectiveness ratio (ICER) will be expressed as the additional cost by life-years gained of a specific strategy (A) in comparison with the next least efficient strategy (B) :

$$\text{ICER} = \frac{\text{Cost of strategy A} - \text{Cost of strategy B}}{\text{Effectiveness of strategy A} - \text{Effectiveness of strategy B}}$$

Robustness of the economic analysis results

To investigate the robustness of the results of the cost-effectiveness analysis, a sensitivity analysis will be carried out by changing some parameters of the study to measure the impact of the variation of these parameters on the final result. The sensitivity analysis will include parameters related to cost data as well as parameters related to effectiveness data.

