Fecal immunological test (FIT) is the reference screening method in average risk patient. FIT is proposed every 2 years to all asymptomatic subjects with average risk aged from 50 to 74 years in France. Optical colonoscopy (OC) is the gold standard examination for patients at increased risk of colorectal cancer, like those with a first degree relative with colorectal cancer (relative risk between 2 and 4 times that of the general population). Colonoscopy should be performed in this high risk group before 50 years or 5 to 10 years before the earliest case of colorectal cancer. Optical colonoscopy has important limitations: complications (perforation, bleeding), need to use general anesthesia (in France 95% of colonoscopy are performed under general anesthesia), and low acceptability for screening even in high risk persons (40% in the best cases). In this high risk population, there is a potentially important place for alternative methods. FIT could be one of them, with already a significant amount of data suggesting its interest. No data are available in high risk French patients. Colon capsule endoscopy (CC) is a more recent technique with sparse data in this high risk group, and no prospective comparison with optical colonoscopy in this indication. Capsule endoscopy has the advantage of high feasibility, very low risk, probably (but to be demonstrated) increased acceptability, and represents the closest examination as compared to colonoscopy. This justifies a prospective study comparing in a randomized methodology these 3 modalities for the identification of advanced neoplastic lesions of the colon in well characterized group of subjects at high risk of colorectal cancer. We propose a prospective, randomized protocol of non-inferiority in order to compare the two new strategies to the reference strategy for the detection of advanced colorectal neoplasia (colon or rectal cancers, large adenoma > 1 cm or high grade dysplasia ; 1st arm: OC first; 2nd arm: CC first, OC at 3 years for those patients with negative initial CC; 3rd arm: annual FIT for 2 years (t_0 , $t = 1$ year, $t = 2$ years), colonoscopy at 3 years for those patients with negative FIT during the study). The new strategies will be considered non-inferior to the reference strategy if the study allows to conclude that the absolute reduction of the proportion of detected patients is not greater than 3% in comparison to the reference strategy.

1- Principal project

SUMMARY

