We propose a prospective, randomized protocol of non-inferiority in order to compare the two new strategies to the reference strategy for the detection of advanced neoplasia. (1st arm: OC first; 2nd arm: CC first, OC at 3 years for those patients with negative initial CC; 3rd arm: annual FIT for 2 years (t_0 , $t = 1$ year, $t = 2$ years), colonoscopy at 3 years for those patients with negative FIT during the study). The strategies will be considered to be equivalent if the 95% confidence interval of the different rate of detected advanced neoplasia won't exceed $\pm 3\%$.

HYPOTHESIS

We make the hypothesis that the results of the two study groups (colon capsule endoscopy and fecal immunological test) will be non-inferior to the results of the control group (optical colonoscopy).

OBJECTIVE

Main objective

To demonstrate the non-inferiority of CC and FIT to OC in terms of efficacy for the detection of advanced colorectal neoplasia (adenoma > 1 cm or with high grade dysplasia, or colorectal cancer any stage).

Secondary objectives

1. Efficacy of each strategy for the detection of colorectal cancer
2. Safety and complications of each screening strategy
3. Cost-effectiveness analysis of the 3 strategies

METHODOLOGY

Study design

Non inferiority multicenter prospective randomized 3 arm study.

We propose a 3 arms prospective, randomized protocol evaluating the sensitivity of 3 strategies for the diagnosis of colon and rectum cancer and advanced neoplasia:

- 1st arm: OC first
- 2nd arm: CC first, OC at 3 years for those patients with negative initial CC
- 3rd arm: annual FIT for 2 years (t_0 , $t = 1$ year, $t = 2$ years), colonoscopy at 3 years for those patients with negative FIT during the study.

The strategies will be considered to be equivalent if the 95% confidence interval of the difference or the detection of advanced neoplasia won't exceed $\pm 3\%$.

Evaluation criteria

Evaluation criteria -> Main objective

The primary endpoint is the prevalence of advanced colorectal neoplasia (adenoma > 1 cm, adenoma with high grade dysplasia) or cancer identified by each strategy after 3 years (expected frequency with the reference examination, *i.e.* colonoscopy: 5,6 %).

Evaluation criteria -> Secondary objectives

The secondary endpoints are:

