The main objective of the study is to compare two alternative methods (CC and FIT) to optical colonoscopy (OC) in term of non-inferiority for the detection of advanced neoplasia. According to the study by Quintero et al, the expected probability of detection of advanced neoplasia by the OC was fixed at 6%. The sample size was calculated for an expected difference between the alternative methods and the colonoscopy of 0 and a delta of non-inferiority of -3%. The method of the unilateral confidence interval of the difference will be used to test the non-inferiority. For each comparison, the unilateral alpha risk, usually fixed at 5%, will be halved in order to take account of the inflation of the type I error due to the multiple testing. For an unilateral alpha risk of 2.5% for each comparison and a power of 80%, **the needed sample size is of 984 patients in each group (total 2952)**. Taking into account 10% lost to follow, the number of patients to be included is 3250 patients in total.

Recruitment

Consecutive first-degree relatives (parents, siblings, or offspring) of patients with non-syndromic CRC referred for screening to the investigator centers will be assessed for enrollment.

Eligible first-degree relatives and index cases will be given a leaflet with detailed information about the study and will be asked to invite any first-degree relatives older than 45 years to participate to the study.

We encouraged them to pass on to their first-degree relatives the leaflet about the study and to stimulate their participation. For this purpose, a contact telephone number will be given to arrange appointments with the study coordinator. We will take advantage of :

- the network of scientific societies to promote the study and inform all members of this protocol, allowing the recruitment of patients through other general/private hospitals into the study
- general practitioner networks of this study to allow a direct recruitment of first degree relatives of colorectal cancer cases
- regional screening structures for breast and colorectal cancer screening to promote the study recruitment by using their registers and contacting patients
- collaboration with private gastroenterology centers who will perform the requested optical colonoscopy for patients included and randomized in the participating centers

Randomization procedure

Central automatized randomization will be used for each screened patient individually, independently of family cluster.

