The main analysis will be carried out in per protocol analysis. In this analysis, only the patients having received the assigned strategy will be considered. All patients with a major deviation to the protocol will be excluded. In the FIT group, the patients complying with at least one of the three screening rounds will be considered for per protocol analysis.

An analysis in intention to treat will also be conducted. In this analysis the patients will be analysed according to their randomisation group, irrespective of whether they will have received or not, the assigned strategy.

The proportion of patients detected with advanced neoplasia by the received strategy at the end of the three years of follow-up will be estimated in each group with its 95% confidence interval.

For each new strategy group (FIT or CCE), the difference of proportion between the group with new strategy and the reference group will be estimated with its 95% bilateral confidence interval. The method of the unilateral confidence interval of the difference will be used for non-inferiority testing. For each comparison, the unilateral alpha risk usually fixed at 5% for one comparison, will be halved and fixed at 2.5% in order to take into account that two comparisons will be carried out. The non-inferiority of the new strategy will be retained if the inferior bound of the confidence interval of the difference is superior to -3%.

3. Analysis for secondary objectives

The efficacy of each strategy for the detection of advanced neoplasia will be estimated on the patients who will have actually received the strategy, whatever their initial randomization group. It will be estimated by the proportion of detected patients at 3 years. They will be estimated with a 95% confidence interval and compared using a chi-2 test or a Fisher exact test.

The observed complications will be described in each group. The proportion of complications will be compared

between the three groups using a chi-2 test or a Fisher exact test.
A bilateral P-value ≤ 0.05 will be considered for statistical significance.
The methodology of the cost-effectiveness analysis is described in a specific paragraph.

STUDY DURATION / CALENDAR

This work needs a 7 years working period including:

- 6 months for study preparation
- 3 years of inclusion
- 3 years of follow-up for all patients before colonoscopy/end of study
- 6 months for data management and analysis, and publication

FEASIBILITY OF THE STUDY

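### The design sections twice state a ±3% equivalence criterion for a trial that is sized and analysed as one-sided non-inferiority at -3%

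*Protocol*

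**What the plan says.** The ±3% rule appears in two places in the Protocol:

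- STUDY DESIGN AND JUSTIFICATION: "The strategies will be considered to be equivalent if the 95% confidence interval of the different rate of detected advanced neoplasia" does not go beyond ±3%.
- METHODOLOGY, Study design: "The strategies will be considered to be equivalent if the 95% confidence interval of the difference or the detection of advanced neoplasia" does not go beyond ±3%.

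The other statements about the primary comparison point in one direction only:

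- Opening abstract: the new strategies count as non-inferior if the study supports the conclusion that the "absolute reduction of the proportion of detected patients is not greater than 3% in comparison to the reference strategy".
- HYPOTHESIS: the capsule and FIT results "will be non-inferior to the results of the control group (optical colonoscopy").
- Main objective: "To demonstrate the non-inferiority of CC and FIT to OC in terms of efficacy for the detection of advanced colorectal neoplasia".
- Number of patients required: the calculation takes "an expected difference between the alternative methods and the colonoscopy of 0 and a delta of non-inferiority of -3" per cent and uses a one-sided confidence interval. "For an unilateral alpha risk of 2.5% for each comparison and a power of 80" per cent, it arrives at 984 per group.
- STATISTICAL ANALYSIS, Non-inferiority analysis: "The non-inferiority of the new strategy will be retained if the inferior bound of the confidence interval of the difference is superior to -3" per cent.

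The hypothesis and objective give no margin. The abstract gives the margin and direction but no confidence bound. The sample size section gives the margin, the one-sided interval method and the alpha. Only the non-inferiority analysis states the bound to be compared with -3%.

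**The concern.** An interval confined to ±3% has two limits, and an interval whose lower bound must exceed -3% has one. The confidence level is the same, since the lower limit of a two-sided 95% interval is the one-sided 97.5% limit. The rules therefore differ only in the upper limit of +3%. They give different verdicts when the lower bound is above -3% and the upper bound is not below +3%.

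That happens when the new strategy is observed to detect more advanced neoplasia than colonoscopy, which is no argument against non-inferiority. Under the design-section wording, such a strategy could still be said to have missed the protocol's criterion. A reader of that section could also expect an equivalence claim, for which the protocol has no objective, no sample size and no analysis.

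**Working it through.** **Inputs.** Number of patients required: colonoscopy rate 6%, true difference 0, margin 3 points, one-sided alpha 2.5% per comparison, power 80%, 984 per group. Evaluation criteria: expected colonoscopy rate 5.6%. Section 1.3: FIT 4.2% and colonoscopy 5.6% in the Spanish randomised study. Normal quantiles: 1.960 (97.5%), 0.842 (80%), 1.282 (90%).

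**1. Reproduce the stated size (one-sided rule).**
n = (1.960 + 0.842)² × 2 × 0.06 × 0.94 / 0.03² = 983.7, so 984 per group. This matches the protocol exactly.

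**2. Size for the ±3% rule.** With a true difference of 0, both limits must hold, so 80% power leaves 10% for failure on each side.
n = (1.960 + 1.282)² × 2 × 0.06 × 0.94 / 0.03² = 1316.9, so 1317 per group.

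**3. Where the rules part at 984 per group.**

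- 6% v 6%: SE = √(2 × 0.06 × 0.94 / 984) = 0.01071 and the 95% half-width is 0.0210. The upper bound reaches +3% once the observed difference exceeds 0.03 - 0.0210 = +0.0090.
- 5.6% v 5.6%: SE = 0.01037 and the half-width is 0.0203. The rules part above +0.0097.

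**4. Probabilities at 984 per group.** With d the true difference (new strategy minus colonoscopy):

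- P(one-sided rule met) = Φ((0.03 + d)/SE - 1.960)
- P(±3% rule met) = Φ((0.03 + d)/SE - 1.960) + Φ((0.03 - d)/SE - 1.960) - 1
- Disagreement = the first minus the second

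At 6% v 6%, 0.03/0.01071 - 1.960 = 0.842 and Φ = 0.800. The ±3% rule then has probability 2 × 0.800 - 1 = 0.600.

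| Colonoscopy v new strategy | One-sided rule met | ±3% rule met | Disagreement |
|---|---|---|---|
| 6% v 6% (sample size section) | 0.800 | 0.600 | 0.200 |
| 5.6% v 5.6% (endpoint section's rate) | 0.825 | 0.650 | 0.175 |
| 5.6% v 4.2% (Spanish study) | 0.376 | 0.371 | 0.005 |

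Exact binomial enumeration with a Wald interval gives the same three disagreement figures.

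**5. Sensitivity, on assumed values that are not in the protocol.** If the new strategy truly detected more than a 6% colonoscopy rate, the disagreement would be 0.370 at +0.5 point and 0.564 at +1 point. These show the direction only.

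**The case against.** The strongest reply is that the governing rule is not in real doubt. The statistical section states it in full, the sample size fits it exactly, and the abstract agrees with it in direction and margin. The section that prints ±3% also calls the trial non-inferiority in its design label, hypothesis and objective. A statistician following the protocol would apply the lower-bound rule.

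A second reply is that the two sentences say when strategies count as equivalent. They do not say that non-inferiority fails once the upper bound passes +3%. On that literal reading the non-inferiority claim survives, and the strategy simply does not earn the label of equivalence.

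A third is that 60% power and 1317 per group describe a rule the trial was never sized for, and that the figures for a truly better strategy rest on invented differences.

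Much of this stands. The sample size and analysis are sound, the power figure is no shortfall of this trial, and the assumed differences should carry no weight. The contradiction remains, however. The ±3% sentence is the only numerical criterion in either design section, and nothing presents it as an additional claim. Read as a separate equivalence claim, it would have no objective, sizing or analysis behind it. On either reading the sentences need changing.

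**Conclusion.** The point holds: the primary decision criterion is wrongly stated in two places. The rules are nested, because any interval inside ±3% also has its lower bound above -3%. The stray rule therefore cannot inflate type I error or create a false non-inferiority conclusion. The harm runs one way: a strategy that satisfies the statistical section may be reported as failing the design section.

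Per comparison, the chance of this is 20.0% under the protocol's own planning values, 17.5% with the 5.6% colonoscopy rate and no difference, and 0.5% at the Spanish study's rates. The figures assume 984 analysed patients per group, independent observations and a Wald interval. This is an inconsistency of wording on the primary criterion that should be corrected; it is not a fault in the design.

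**What to change.** Replace both ±3% sentences, under STUDY DESIGN AND JUSTIFICATION and under METHODOLOGY, Study design, with one rule matching the statistical section. For example: a new strategy is declared non-inferior to colonoscopy if the lower limit of the two-sided 95% confidence interval (equivalently, the one-sided 97.5% limit) for the difference in detection proportions, new strategy minus colonoscopy, is greater than -3 percentage points. Use the term non-inferior, not equivalent, in both places.

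The cost is two sentences of protocol text. The sample size stays at 984 per group with 80% power, and data collection and analysis do not change.

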Patient follow-up

- 1st arm: OC first, then annual follow-up for 3 years by phone call.
- 2nd arm: CC first, yearly follow-up for 3 years by phone call, OC at 3 years for those patients with negative initial CC.
- 3rd arm: annual FIT yearly for 2 years (t_0 , $t = 1$ year, $t = 2$ years) and yearly follow-up for 3 years by phone call, OC at 3 years for those patients with negative FIT during the study.
- Pathological examination of detected and resected colorectal neoplasia will follow the usual conditions of pathological examination. There will be no centralized pathological analysis.

Measured parameters

The following data will be recorded: number and age of the index case(s) with colorectal cancer; number, size and dysplasia of neoplastic colorectal lesions; toxic habits (tobacco, alcohol); BMI; type of familial link (parent, offspring and siblings) with the index case; pathological characteristics of neoplastic lesions. Quality assessment of colonoscopy and capsule endoscopy (caecal intubation rate; capsule completion rate with rectal visualization and capsule excretion).

Blinding

Pathological analysis of colorectal lesions will be performed blindly.

Supply of medical devices

The colon capsules needed for the study will be graciously provided by MEDTRONIC, which will deliver them directly to the reference centers upon demand.

The FIT kits needed for the study will be graciously provided by MAST DIAGNOSTIC, which will dispatch them to the reference centers upon demand.

FIT analysis will be carried out by the Laboratory of Functional Coprology (Pitié-Salpêtrière Hospital) on a measuring device and with reagents both graciously provided by MAST DIAGNOSTIC.

STATISTICAL ANALYSIS

1. Descriptive analysis

The quantitative characteristics of the patients will be described in each group by the mean and the standard deviation, or by the quartiles and the minimum and maximum values according to the shape of the distribution. The qualitative characteristics of the patients will be described in each group by the absolute and relative frequency. The comparisons between the 3 groups will be carried out using an analysis of variance or the Kruskal Wallis test for the quantitative characteristics, and using the chi-2 test of homogeneity or the Fisher exact test for the qualitative characteristics.

2. Non-inferiority analysis

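### 3250 patients less the stated 10% loss leaves 975 per arm, not the required 984, and the allowance names only loss to follow-up although the main analysis is per protocol (minor)

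*Protocol*

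**What the plan says.** Under Number of patients required, the protocol fixes the colonoscopy (OC) detection rate at 6%, a true difference of 0, a margin of 3 percentage points, a one-sided alpha of 2.5% per comparison and 80% power. It concludes that "the needed sample size is of 984 patients in each group (total 2952"). The next sentence sets enrolment: "Taking into account 10% lost to follow, the number of patients to be included is 3250 patients in total". The feasibility section uses 3250 as well.

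Under Evaluation criteria, Main objective, the primary endpoint comes with a slightly different rate: "expected frequency with the reference examination, *i.e.* colonoscopy: 5,6" %.

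Under Statistical analysis, 2. Non-inferiority analysis, "The main analysis will be carried out in per protocol analysis". In that set "only the patients having received the assigned strategy will be considered", and "All patients with a major deviation to the protocol will be excluded". For the FIT arm, "the patients complying with at least one of the three screening rounds will be considered for per protocol analysis". Under Patient follow-up, the reference arm has "OC first, then annual follow-up for 3 years by phone call".

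**The concern.** There are two points in one sentence.

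First, 984 per arm is a requirement for patients analysed. Enrolment should therefore be the number that still leaves 984 per arm after the stated loss. It is not, so two adjacent sentences disagree.

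Second, the 80% power is a statement about the primary analysis set. That set is per protocol and is reduced by non-receipt of the strategy and by major deviations. The allowance is named for loss to follow-up, and no other allowance appears in the protocol. The loss that was planned for and the loss that determines the primary set are therefore described differently.

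At stake is whether the stated enrolment supports the stated power for the analysis on which non-inferiority will be judged.

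**Working it through.** **Inputs.** From Number of patients required: p = 0.06 in both arms, margin 0.03, one-sided alpha 0.025 (z = 1.960), power 80% (z = 0.842), 984 per arm, 2952 in total, 10% loss, 3250 enrolled. From Evaluation criteria: p = 0.056. Equal arms and a true difference of 0 throughout, with the unpooled normal approximation.

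**Step 1: reproduce the plan's figure.**
n per arm = 2p(1−p)(1.960 + 0.842)² / 0.03², where the squared sum is 7.849 before rounding of the z values.
- p = 0.06: 0.1128 × 7.849 / 0.0009 = 983.7, so 984. The protocol's figure is confirmed.
- p = 0.056: 0.105728 × 7.849 / 0.0009 = 922.1, so 923.

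**Step 2: the inflation.**
- 2952 × 1.10 = 3247.2, which rounds to the stated 3250.
- 2952 / 0.90 = 3280 (3282 if each arm is rounded up to 1094).
- 3250 × 0.90 = 2925 = 3 × 975. The shortfall is 2952 − 2925 = 27 patients, 9 per arm.
- Largest loss that still leaves 984 per arm: 1 − 2952/3250 = 9.2%.

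**Step 3: power with 975 per arm.**
Power = Φ(0.03 / √(2p(1−p)/n) − 1.960).
- p = 0.06: SE = √(0.1128/975) = 0.010756; 0.03/0.010756 = 2.789; Φ(0.829) = 79.6%. With 984 per arm the same formula gives 80.0%, so the loss is about 0.4 points.
- p = 0.056: SE = √(0.105728/975) = 0.010413; 0.03/0.010413 = 2.881; Φ(0.921) = 82.1%.

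**Step 4: how power depends on the total share not evaluable, starting from 3250.** Only the 10% stands in the protocol, and there as loss to follow-up. The 9.2% is the limit from Step 2. The 0%, 15% and 20% rows are assumed, with equal loss in all arms.

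| Not evaluable | n per arm | Power at 6% | Power at 5.6% |
|---|---|---|---|
| 0% (assumed) | 1083.3 | 83.6% | 85.9% |
| 9.2% (limit) | 984 | 80.0% | 82.5% |
| 10% (stated) | 975 | 79.6% | 82.1% |
| 15% (assumed) | 920.8 | 77.4% | 79.9% |
| 20% (assumed) | 866.7 | 74.8% | 77.5% |

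**Step 5: which losses leave the per-protocol set?** Non-receipt of the strategy and major deviations come out and are not named in the allowance, which pushes the evaluable number down. In the other direction, a patient who has had the entry colonoscopy and is later lost to the annual calls may still count as having received the strategy, and a FIT patient needs only one round of three. Some of the 10% lost to follow-up may therefore remain in the primary set. The protocol gives no rate for either flow, so the net effect cannot be calculated.

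**The case against.** The strongest reply is that nothing depends on this. Nine evaluable patients per arm is under 1% of 984, and 3250 is a rounded recruitment target. The multiplication by 1.10 is inferred from the result, since the protocol does not state its method. At the 5.6% given with the primary endpoint, 923 per arm are enough and 975 exceeds that. *Lost to follow* could also be loose shorthand for every patient who is not evaluable.

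Most of this stands. The size is trivial, and the 5.6% rate removes the shortfall. What remains is that the calculation is fixed at 6%, and at that rate the enrolment does not deliver the protocol's own 984 per arm under its own 10%. That holds whichever method produced 3250.

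A reader might infer more: that the trial is underpowered, or that per-protocol exclusions will take power well below 80%. The document supports neither. Power at the stated loss is 79.6% or 82.1%. The lower figures in the table rest on exclusion rates that the protocol does not give, and its rules for the primary set may retain patients whom the allowance counts as lost. If the shorthand reading is intended, the sentence should say so.

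**Conclusion.** The sentence is wrong as written, and the point is minor. Under the stated 10% loss, 3250 gives 975 per arm where 984 are required. This costs about 0.4 points of power at 6% (79.6%) and nothing against the 80% target at 5.6% (82.1%). The target of 984 per arm holds only up to 9.2% total loss.

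The mismatch between the named loss and the per-protocol primary set is real, but its size and direction are not determined by the protocol. These figures assume a true difference of zero, equal loss in all arms and the normal approximation that reproduces the 984.

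**What to change.** Keep 3250 and replace the enrolment sentence with:

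> 3250 patients will be included; if 10% of patients in each arm are not evaluable for the per-protocol analysis for any reason (planning assumption), 975 per arm remain, giving 79.6% power at a 6% detection rate (82.1% at 5.6%); 80% power at 6% holds up to 9.2% non-evaluable.

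The words *planning assumption* are needed because the protocol supports 10% only as loss to follow-up, not as a total per-protocol exclusion rate. Power at 15% or 20% may be added but must be labelled as assumed.

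The cost is wording only; enrolment, design and analysis do not change. If the sponsor prefers to keep the full 80% at 6% with 10% non-evaluable, the number to include is 3280, or 30 more patients (3282 with whole numbers per arm), and the feasibility section would then need the same figure.
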